### 4 STUDY DESIGN

#### 4.1 Study Overview

This study will be a single center, randomized double-blind placebo-controlled trial designed to assess the effect of daily 1200 mg ALA supplementation for three years on kidney stone recurrence in participants with cystinuria. Participants will be computer sequence-randomized to receive either oral daily dosing of 1200 mg ALA or placebo. Participants will be allowed to continue potassium citrate treatment, the currently mainstay of cystinuria treatment, so as to avoid inducing worsened clinical events. If participants are taking D-penicillamine and alpha-mercaptopropionylglycine at the time of study enrollment, they will be asked to stop these medications 12 weeks prior to starting the treatment portion of the study as a washout period to ensure no harmful effects result

from stopping these therapies. If they chose not to stop, at the discretion of the Principal Investigator, the participant will be allowed to participate and the study will simply document the use of Thiola throughout the course of the study. A minority of cystinuric stone formers take D-penicillamine and alpha- mercaptopropionylglycine and our clinical experience reflects that these medications do not demonstrate a high efficacy for stone prevention. We therefore do not think that stopping these drugs will worsen clinical stone outcomes, but to ensure this is the case, participants who are on these medications and choose to stop, will be observed for a 12-week washout period after stopping D-penicillamine and alpha-mercaptopropionylglycine and prior to starting ALA. We anticipate participant enrollment to last 6-8 months. The secondary objectives of this study are to determine the effect of ALA on quantitative urinary cystine, cystine solubility, and metallomic and metabolomics profiles in participants with cystinuria to help determine the mechanism(s) of action of ALA in cystinuric individuals. Both study participants and study team members will be blinded to the treatment.

Clinical data including medical history, plain KUB x-ray and renal ultrasound, routine blood work, and 24-hour urine collections for all participants will be collected as part of normal clinical care at routine clinical visit intervals, which currently occur every 4 months. Routine clinical care for participants will not be altered in any way outside of administration of the supplement or placebo. Routine clinical care generally consists of office visits every 4 months at which time, as medically necessary as determined by the study investigator, an imaging study is performed (plain KUB x-ray, ultrasound, or CT scan if clinically indicated), a 24-hour urine collection is done to check quantitative urinary cystine levels, and blood is drawn to evaluate electrolyte levels as well as renal function. During routine visits for blood and urine tests, any discarded blood and urine specimens will be collected for research testing. No additional blood draw or urine collection will be performed for this study. From discarded routine specimens provided during these clinic visits, metallomic and metabolomics profiling will be performed for all participants using discarded samples material. This is comprised of mass spectrometry and elemental analysis of samples performed in our research lab. Quality of life measurement, as recorded by the Wisconsin Stone-quality of life questionnaire (Wisconsin Stone-QoL), will also be evaluated.

Recurrent stone events, defined by symptomatic or silent stone recurrence, is the primary endpoint in this study. It will be documented in this study cohort, and compared between treatment and placebo groups to determine treatment effect. If stones are removed for surgery or spontaneously passed by participants, any discarded stone specimens not needed for clinical care will also be subjected to metabolomic and metallomic analysis.

At the end of the three years of study drug treatment, all participants will undergo a low dose non-contrast CT scan to look for a silent change in stone size. As this is a pilot study, recruitment will be limited to target enrollment of 50 participants (25 for each treatment arm). Treatment will continue for a total of 3 years and after treatment completion, participants will be followed for an additional 2 years to evaluate for change in clinical status or adverse events resultant from ALA administration.

## 5 CRITERIA FOR EVALUATION

### 5.1 Primary Efficacy Endpoint

The primary efficacy endpoint will be assessed in two ways over the course of the 3-year treatment period:

1) Symptomatic stone recurrences, defined as renal colic, stone passage, or surgical removal of a stone

2) Silent stone recurrences, classified as stone growth or new stones, diagnosed on the basis of renal ultrasound, abdominal flat-plate examinations, or if clinically indicated, computed tomography.

These clinical endpoints are already collected as a part of the participants' routine clinical care and exist as part of their medical record. Data will simply be abstracted from clinical encounters.

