At present we can only hypothesize on the possible mechanism(s) of action of ALA. First, ALA may modulate intracellular cysteine levels through its effects on the cystine/glutamate exchanger and thereby increase glutathione production. Second, ALA may counteract oxidative stress by induction of nuclear factor erythroid related factor 2 (Nrf2), which is involved in cellular cystine uptake. Third, ALA may directly reduce insoluble cystine to form a mixed-disulfide compound to increase urinary solubility of cystine. Fourth, ALA may reduce zinc levels in the kidney, which has been identified as a cofactor in stone formation. No matter which mechanism(s) ultimately emerge(s) as the appropriate explanation, we believe that oral administration of lipoic acid will decrease the amount of quantitative urinary cystine and, most critically, slow the rate of stone formation and growth, thereby reducing the frequency of stone events in cystine stone formers.

In our lab, a mouse model of cystinuria lacking the *Slc3a1* gene was employed to study the formation and growth of urinary cystine stones. *Slc3a1*-/- male mice develop cystine stones at about 2-3 months of age and accumulate stone volume at an approximate rate of 1 mm^3/day, measured by micro-computed tomography. In initial work, 1-month old *Slc3a1*-/- mice were treated with ALA administered through supplementation in the diet (0.5% by weight). By day 45, 1 of 8 mice on the ALA-supplemented diet had developed stones, in contrast to 7 of 7 control mice fed a regular chow diet. In addition, 3-month old untreated stone-forming mice that were then fed ALA grew cystine stones at a dramatically slower rate (stone volume accumulation 10% of controls, n=9) over 120 days. In summary, these initial results show that ALA markedly slows the initiation of cystine stone formation as well as the growth of existing stones. Moreover, based upon body weight, feeding behavior and activity level ALA appears to be very well tolerated in the mouse.

To date, there have been no published studies on the effect of ALA in human stone formers.

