## 6.2 Inclusion Criteria

Inclusion criteria will include: males and females age 18 or older; documented cystinuria on prior 24-hour urine collection and/or stone analysis; history of previous cystine kidney stones; and being able and willing to provide consent.

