### **9.1.6 Other Clinical Procedures**

Imaging studies will be performed at scheduled clinic visits as medically needed and at the discretion of the investigator. The imaging studies may include plain KUB x-ray and renal ultrasound, or CT scan if medically necessary (see below). This information will allow determination of silent stone recurrences classified as stone growth or new stones compared to prior radiologic exams. All participants will undergo low dose non-contrast CT scans at the end of the three years of study drug treatment (Visit10). This non-contrast CT scan at the end of the three-year study period will be considered a research imaging study (not a part of routine clinical care) and paid for by study funding.

In addition, quality of life surveys with Wisconsin Stone-QoL will be administered during regularly scheduled clinic visits.

If participants collect stones that pass during the course of the study, these will also be collected and analyzed for composition.

All of these clinical procedures are part of the current standard of care for patients with cystinuria undergoing management at UCSF with the exception of the CT scan performed at the completion of the study. With the exception of this radiographic study, the current study will not alter standard clinical care for participants.

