### **15.2 Analysis of Primary Endpoint**

The primary efficacy endpoint will be assessed in two ways over the course of the 3-year treatment period: 1) symptomatic stone recurrences, defined as renal colic, stone passage, or surgical removal of a stone; and 2) silent stone recurrences classified as stone growth or new stones, diagnosed on the basis of renal ultrasound, plain KUB x-ray, or if clinically indicated, CT scan. The analysis will be performed on the intention-to-treat principle in the treatment and placebo groups.

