**APPENDIX 1. SCHEDULE OF STUDY VISITS**

	VISIT 1 (Initial Visit)	VISITS 2-9 (Month 4-32)	VISIT 10 (Month 36)	VISITS 11-16 (Month 40-56)
Informed Consent	X			
Medical History	X	X	X	X
Complete Physical Exam	X			
Abbreviated Physical Exam		X	X	X
Vital Signs	X	X	X	X
Wisconsin Stone-QoL survey	X	X	X	X
Record any Adverse Experiences		X	X	X
Concomitant medications review	X	X	X	X
Pill Count		X	X	X
Collect routine blood for clinical laboratory tests (CBCs, chemistries, BUN, creatinine).	If medically indicated	If medically indicated	If medically indicated	If medically indicated
Perform routine 24hr urine testing	X	X	X	X
Perform routine plain KUB x-ray and renal ultrasound	If medically indicated	If medically indicated	If medically indicated	If medically indicated
Perform low-dose CT abdomen	If medically indicated	If medically indicated	X	If medically indicated
Collect discarded blood and urine for research purposes, if presented	X	X	X	X
Collect passed stone specimens, if presented	X	X	X	X

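### The symptomatic endpoint counts a stone removal already planned before randomisation as a recurrence, which modestly dilutes the treatment effect

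*Combined protocol and SAP*

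**What the plan says.** Section 5.1 gives the symptomatic component as "Symptomatic stone recurrences, defined as renal colic, stone passage, or surgical removal of a stone", and Section 15.2 carries it into the analysis: "symptomatic stone recurrences, defined as renal colic, stone passage, or surgical removal of a stone". The Synopsis and Sections 3.1 and 9.1.3 use the same three limbs. Section 4.1 combines the two components: "Recurrent stone events, defined by symptomatic or silent stone recurrence, is the primary endpoint in this study".

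Only the silent component is tied to an earlier state of the kidney. Section 9.1.6 describes "silent stone recurrences classified as stone growth or new stones compared to prior radiologic exams".

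On stone status at entry, Section 6.2 asks only for "history of previous cystine kidney stones; and being able and willing to provide consent" besides age and documented cystinuria. Section 6.3 excludes neither stones in place nor a planned procedure. On ascertainment, Section 5.1 says "Data will simply be abstracted from clinical encounters", and no adjudication is described. Section 4.1 states that routine care is unchanged apart from the supplement or placebo, so a booked operation would go ahead. Section 15 promises a later, detailed SAP, but nothing in the current text addresses the point.

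**The concern.** The primary objective is the effect of ALA on recurrence. The word symptomatic does not supply a symptom test, because the protocol defines the term by its list and the limbs are joined by *or*. Two participants then score alike:

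- One has a stone known at Visit 1 with removal already booked. It is removed in month 2 without symptoms, and no new stone appears to month 36. Score: 1 event, or 1/3 = 0.33 per year.
- One forms a stone at month 14 that causes colic. Score: 1 event, or 0.33 per year.

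The second is what the trial sets out to prevent. The first was settled before the first dose. Counting both pulls the estimated relative reduction toward zero and adds variance in a trial of 25 per arm.

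**Working it through.** **Inputs from the documents.** Control rate 1 event per person-year; 50% reduction, a difference of 0.5 per year; two-sided alpha 0.05; 90% power; SD scenarios 0.5, 0.75 and 1 (Section 15.3). t-test on rates (Synopsis). 25 per arm (Section 4.1). Three-year endpoint window (Section 5.1). No dropout is applied here, because the plan calls it small and gives no figure.

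**Input not in the documents.** The share p of participants who have one removal already planned at randomisation. I assume p = 10% and p = 50% to show a range.

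**The plan's own figures.** Section 15.3 states n = 11, 24 and 42. The formula (SD × (1.960 + 1.282) / 0.5)² gives 10.51, 23.64 and 42.03, which matches, but it is the one-sample form. A two-arm t-test needs 22, 48 and 85 per arm (exact solutions 22.02, 48.26 and 85.03). That is a separate matter. Here I take power at the planned 25 per arm as the starting point: 93%, 64% and 41% for SD 0.5, 0.75 and 1.

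**Model 1: the planned removals are part of the 1 event per year.** ALA halves only the rest. With f = p/3 as their share of the control rate, the difference is 0.5 × (1 − f) and the SD is unchanged.

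- p = 10%: f = 0.10/3 = 0.033; difference 0.5 × 0.967 = 0.483.
- p = 50%: f = 0.50/3 = 0.167; difference 0.5 × 0.833 = 0.417, an apparent reduction of 42%.

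**Model 2: they come on top of the planned rate, independently of other events.** The difference stays 0.5 and the variance of the three-year mean rate rises, by p(1 − p)/9 if each person has 0 or 1 such event, or by p/9 if the count is Poisson.

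- p = 50%: added variance 0.25/9 = 0.028 or 0.50/9 = 0.056. SD 0.5 becomes 0.527 or 0.553; SD 0.75 becomes 0.768 or 0.786. The relative reduction appears as 0.5/1.167 = 43%.
- p = 10%: added variance 0.09/9 = 0.010 or 0.10/9 = 0.011.

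Two-sample t-test power at 25 per arm:

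| Assumption | Difference per year | SD 0.5 | SD 0.75 | SD 1 |
|---|---|---|---|---|
| No such events | 0.500 | 93% | 64% | 41% |
| 10% have one, within the planned rate | 0.483 | 92% | 61% | 39% |
| 10% have one, on top of it | 0.500 | 92% | 63% | 41% |
| Half have one, within the planned rate | 0.417 | 82% | 49% | 30% |
| Half have one, on top of it | 0.500 | 88-91% | 60-62% | 39-40% |

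The documents do not show which model applies, since that depends on what the cited rate of 1 per year counted.

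**The case against.** The strongest case for leaving the rule alone is that, in a randomised and blinded trial, counting every procedure after randomisation is a defensible intention-to-treat choice. These events fall equally on both arms in expectation. That stands, and it limits the harm to dilution and noise, with chance imbalance possible at 25 per arm.

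Four stronger readings are tempting, and the documents do not support them.

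- **A reader might infer that any removal of a stone present at entry is beyond the drug's reach.** Section 2 says otherwise. It expects ALA to "slow the rate of stone formation and growth, thereby reducing the frequency of stone events in cystine stone formers", and reports that stone-bearing mice on ALA accumulated stone volume at 10% of the control rate. A later removal prompted by growth on study could respond to treatment. Only what was settled before the first dose is surely unpreventable.
- **A reader might assume that 10% to 30% of events are of this kind**, which under Model 1 takes power down to 68% at SD 0.5. Over three years at 1 event per year, those shares mean 0.3 to 0.9 already-fixed events per participant. Nothing in the documents supports that.
- **A reader might want to drop symptom-free removals of entry stones that have not grown.** Growth after randomisation is something ALA may change. The same elective removal would then be excluded more often on ALA and counted more often on placebo, which favours ALA. The rule would also need baseline imaging. Section 10.1 lists none, and Appendix 1 makes "Perform routine plain KUB x-ray and renal ultrasound" at Visit 1 conditional on medical need.
- **A reader might infer a risk of a false early stop**, because planned procedures tend to come early and weigh more at the interim look. Events expected equally in both arms do not make a false efficacy finding more likely.

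**Conclusion.** The point holds for one class of event: removal of a stone by a procedure already scheduled or recommended before randomisation. As written, it counts as a symptomatic recurrence even without symptoms, and no other section prevents this.

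The cost is probably modest. It is 1 to 3 percentage points of power if 10% of participants have one such procedure. If half do, the loss is 11 to 15 points under Model 1 at SD 0.5 and 0.75, and about 2 to 5 points under Model 2. All of this rests on an assumed frequency. The missing two-arm factor in the sample size matters more at SD 0.75 and 1. The change is still worth making: the rule turns on a fact known before treatment, costs little, and brings the count closer to the stated objective.

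**What to change.** In Sections 5.1 and 15.2, state that the primary event total does not include removal of a stone by a procedure documented as scheduled or recommended at randomisation, including its planned later stages. Then:

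- Add a Visit 1 field for any such procedure, completed before treatment starts. Section 10.1 now records past surgical interventions but not planned ones.
- Classify events against that field blinded to arm.
- Report the excluded events by arm.
- Keep the all-events count as a sensitivity analysis.
- Do not use growth after randomisation as an exclusion condition. Removals of other stones present at entry stay in the primary count.

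The rule should be fixed before any unblinded look, including the interim analysis. It costs one extra data field and slightly fewer counted events. It needs no added imaging and does not change care.

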### 5.2 Safety Evaluations

After participants are enrolled at 3-4 weeks during the treatment period, a study coordinator will contact each participant to check compliance, tolerability, and side effects with ALA supplementation. Any concern for a potential adverse event will be reviewed by the study investigators. In addition, tolerability and side effects will be reviewed at each scheduled, four-month clinic visit. All adverse events will be reviewed by the study investigators. Depending on the severity of the adverse event, the study investigator may determine the need for un-blinding, and the participant may be advised to stop ALA intake if it is determined that ALA is the cause.

In addition, during the informed consent process, all potential side effects and drug interactions will be discussed. Enrolled participants will be provided the email address of the study coordinator and a 24-hour contact phone number of a physician if any adverse events occur during the study period.

When 50% of participants have been in the study for 6 months, an interim analysis will be performed. If it is found that clinical outcomes for ALA-treated participants are significantly improved compared to the placebo arm, study investigators may elect to complete the trial early and provide all participants with ALA.

## 6 PARTICIPANT SELECTION

### 6.1 Study Population

Participants with a diagnosis of cystinuria who meet the inclusion and exclusion criteria will be eligible for participation in this study.

## 6.2 Inclusion Criteria

Inclusion criteria will include: males and females age 18 or older; documented cystinuria on prior 24-hour urine collection and/or stone analysis; history of previous cystine kidney stones; and being able and willing to provide consent.

## 6.3 Exclusion Criteria

Exclusion criteria will include: poorly controlled diabetes mellitus (hemoglobin A1C > 8.0% for more than 1 year); current ALA administration at the time of screening; ALA administration within the last year prior to screening; vulnerable populations including incarceration status; anticipation of pregnancy during the study duration; unable to give informed consent; non-English primary language; pregnancy, lactation, or child-bearing age without birth control devices; and serious illness likely to cause death within the next 5 years.

## 7 CONCURRENT MEDICATIONS

All participants should be maintained on the same medications throughout the entire study period with no introduction of new chronic therapies, as medically feasible.

### 7.1 Allowed Medications and Treatments

No medications will be strictly prohibited. However, alpha-mercaptopyrionylglycine and D-penicillamine, two medications currently used to treat cystinuria, are both thought to bind the sulfhydryl groups of cysteine preventing the molecules from binding together resulting in the insoluble cystine molecule. Both medications are not used with great frequency and both are not very effective. As they may interfere with the mechanism of action of ALA, participants of this study who take alpha-mercaptopyrionylglycine and/or D-penicillamine will be asked to stop these medications 12 weeks prior to starting the treatment portion of the study as a washout period to ensure no harmful effects result from stopping these therapies. If they choose not to, at the discretion of the Principal Investigator, the participant will be allowed to participate and the study will simply document the use of Thiola throughout the course of the study and may look at these participants separately in the final analysis. .

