PRIMARY ENDPOINT	
The primary efficacy endpoint will be assessed in two ways over the course of the 3-year treatment period:
 
 
1) symptomatic stone recurrences, defined as renal colic, stone passage, or surgical removal of a stone;
 
2) silent stone recurrences, classified as stone growth or new stones,
 

	diagnosed on the basis of renal ultrasound, plain KUB x-ray, or if clinically indicated, computed tomography.
SAFETY EVALUATIONS	After participants are enrolled at 3-4 weeks during the treatment period, a study coordinator will contact each participant to check compliance, tolerability, and side effects with ALA supplementation. Any concern for a potential adverse event will be reviewed by the study investigators. Patient clinical care will continue as per the current standard for the duration of this study. Tolerability and side effects will be reviewed at each scheduled clinic visit which normally occur every four months. All reported adverse events will be reviewed by the study investigators. Depending on the severity of the adverse event, the study investigator may determine the need for un-blinding, and the participant may be advised to stop ALA intake if it is determined that ALA is the cause.
PLANNED INTERIM ANALYSES	When 50% of target participants have been enrolled and on the study protocol for 6 months, an interim analysis will be performed by an un-blinded statistician to evaluate for ALA clinical effects.
STATISTICS Primary Analysis Plan	The analysis will be performed on the intention-to-treat principle in the treatment and placebo groups. The primary efficacy endpoint will be assessed by comparing the rates of symptomatic and silent stone recurrences using the t-test with a two-sided p-values and calculated 95% confidence intervals. In addition, the analysis of secondary endpoints will compare quantitative urinary cystine, and metallomic and metabolomics profiles using repeated measures of analysis of variance.

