## 8 STUDY TREATMENTS

### 8.1 Method of Assigning Participants to Treatment Groups

Participants will be computer sequence-randomized to receive either oral daily dosing of 1200 mg ALA or placebo.

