### 15.3 Sample Size and Randomization

The target enrollment for this study is 50 participants, based on a conservative approach to determine the sample size needed to evaluate the effect of ALA supplementation. Two recent studies evaluating the medical management of cystinuric individuals have reported that among individuals who are compliant in taking medications, the average number of stone events per person is approximately 1 per year (Reference #'s 5, 9). The current study design will be powered at 90% to detect a clinically meaningful reduction of stone events at 50% (0.5 stone events per year) with two-tailed  $\alpha = 0.05$ . Based on a two-sided t- test, the following scenarios were considered for the standard deviation (SD) for the sample and sample size (n): SD 0.5, n=11; SD 0.75, n=24; SD 1, n=42. To account for a small dropout rate over the study duration, the enrollment of 50 participants was proposed. At UCSF, clinical volume approximates 60 nephrolithiasis patients per week, including those with cystinuria. At a recent cystinuria outreach event led by [name] at UCSF (<http://[name].ucsf.edu/?q=news/june-18-2015-cystine-patient-symposium>), over 50 individuals with cystinuria attended among over 100 participants overall. We anticipate that 6-8 months will be required to accrue these participants.

Participants will be computer sequence-randomized to receive either ALA or placebo.

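### Continuing thiol users, in whom the protocol suspects interference with ALA, are pooled unadjusted with an optional separate look, so the ALA effect may be diluted and the split can be chosen after the results

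*Combined protocol and SAP*

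**What the plan says.** Section 7.1 and the synopsis name two drugs, D-penicillamine and alpha-mercaptopropionylglycine. "As they may interfere with the mechanism of action of ALA", users are asked to stop 12 weeks before study treatment. Those who choose not to may still take part at the Principal Investigator's discretion, and the study "may look at these participants separately in the final analysis". Section 4.1 repeats the arrangement but omits even the optional separate look; there, "the study will simply document the use of Thiola throughout the course of the study".

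Assignment is covered in one sentence of Section 8.1: "Participants will be computer sequence-randomized to receive either oral daily dosing of 1200 mg ALA or placebo". Section 15.3 says the same. Neither mentions a stratification factor or blocks. Section 8.2 places randomisation at the first screening visit.

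On analysis, Section 15.1 includes everyone enrolled and Section 15.2 adopts intention to treat. The synopsis names the method: "comparing the rates of symptomatic and silent stone recurrences using the t-test". No covariate appears anywhere. Section 15 promises a detailed SAP before the final data are analysed. Sections 5.2 and 8.2 provide for an interim look that can end the trial early; neither mentions thiol use.

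**The concern.** The protocol itself identifies a possible effect modifier, admits people who carry it, and then controls for it neither at assignment nor in the analysis. Three consequences follow, and they need different remedies.

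- **Dilution.** If ALA works less well in continuing users, the pooled difference averages a larger and a smaller effect. The sample size makes no allowance for this.
- **Imbalance.** With 50 people and a factor carried by few of them, the arms can differ noticeably in thiol use by chance. If thiol use, or whatever leads someone to decline to stop, is related to the stone rate, the estimate becomes less precise and a single realised trial can mislead.
- **Optional reporting.** An analysis that may or may not be done, with no definition of the groups, can be kept or dropped once the results are visible. This holds whatever the prevalence of thiol use or the size of any interference.

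**Working it through.** **Inputs from the documents.** 25 per arm (Section 4.1). Two-sided alpha 0.05, 90% power, and SD scenarios 0.5, 0.75 and 1 (Section 15.3). Control rate: "the average number of stone events per person is approximately 1 per year". Target difference: 0.5 events/year.

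**Assumptions, because the documents give no figure.** The share f who continue is 10% or 20%; Section 4.1 says only that a minority of patients take these drugs. ALA has either no effect or half its effect in those who continue. There is no dropout, and the SD stays at the plan's value.

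**The plan's own figures.** The stated n of 11, 24 and 42 match (SD × (1.960 + 1.282) / 0.5)² = 10.5, 23.6 and 42.03, which is a one-sample formula. The two-sample version doubles this and gives 22, 48 and 85 per arm. That is a separate and larger issue. It matters here because it sets the undiluted baseline: at 25 per arm, 90% power is reached only at SD 0.5.

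**Dilution.** With full interference, pooled difference = 0.5 × (1 − f). With half interference, it is 0.5 × (1 − f/2). Power comes from the two-sample noncentral t with 48 degrees of freedom and noncentrality = difference / (SD × √(2/25)).

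| Scenario | Difference | SD 0.5 | SD 0.75 | SD 1 |
|---|---|---|---|---|
| No interference | 0.50 | 93% | 64% | 41% |
| f = 10%, full; or f = 20%, half | 0.45 | 88% | 55% | 34% |
| f = 20%, full | 0.40 | 79% | 46% | 28% |

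**Non-users only.** With f = 20% split 5:5, 20 per arm remain and the difference is 0.50. Power is 87%, 54% and 34%. This is better than the fully diluted pooled test (79%, 46%, 28%) but worse than the pooled test if there is no interference (93%, 64%, 41%). That supports using it as a sensitivity analysis rather than as the primary one.

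**Imbalance.** Assume 10 continuing users and a fixed 25/25 allocation. The number x in one arm has probability C(10,x) × C(40,25−x) / C(50,25).

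- 7:3 or worse: 29%
- 8:2 or worse: 7% (11% if assignment is simple and unblocked)

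A 7:3 split is 7/25 − 3/25 = 28% − 12% = 16 percentage points. If continuing users differed in stone rate by an assumed 0.5 events/year, the unadjusted difference would shift by 0.16 × 0.5 = 0.08 events/year. The standard error of the arm difference, SD × √(2/25), is 0.14, 0.21 and 0.28 at the three SDs. The shift is therefore about 0.6, 0.4 and 0.3 standard errors. If thiol use is not prognostic, the shift is zero.

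**What an interaction contrast can show.** With 5 users and 20 non-users per arm and full interference, the contrast is 0.5 and its standard error is SD × √(2/20 + 2/5) = 0.35, 0.53 and 0.71. Power is about 28%, 15% and 11%.

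**The case against.** The strongest defence is that the effect is probably small. Users are asked to stop by default, and continuing needs the investigator's agreement, so continuing users are a subset of what is already a minority. The protocol calls the drugs not very effective, which points to weak prognostic value. Section 9.1.1 has all concomitant medication recorded at baseline and at every visit, so the later SAP could adjust for thiol use. In a 50-person trial that describes itself as a pilot, stratifying on one infrequent factor is a choice, not a requirement.

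Much of this stands, and it rules out stronger readings that a reader might infer.

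- *That the ALA effect is diluted.* The documents say only that the drugs may interfere. They give neither a size nor a number continuing.
- *That the comparison is confounded.* Under randomisation, chance imbalance adds variance; it does not bias the estimate on average. The documents do not say that continuing users are more severe stone formers.
- *That no later analysis could help.* Adjusting for a recorded baseline factor would deal with imbalance in it. What is missing is the commitment to do so.

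The defence does not answer the optional wording. The promised SAP need only precede the final analysis, so it may come after the interim look, and nothing says that it will cover thiol use. A low opinion of the drugs' own benefit also does not remove the protocol's stated worry about interference.

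**Conclusion.** The point holds in conditional form. The plan names a possible effect modifier, leaves it unbalanced and unadjusted, and makes the only relevant analysis optional. The selective-reporting risk follows from the text alone.

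Dilution and imprecision are possible but cannot be sized from the documents. The drop to 79%, 46% and 28% power rests on an assumed 20% continuing and complete loss of effect in them; at 10% continuing, power is 88%, 55% and 34%. At SD 0.75 and 1, most of the power shortfall exists before any dilution. The 29% chance of a 7:3 or worse split matters only as far as thiol use is prognostic. The change is worth making because it costs almost nothing, not because serious harm has been shown.

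**What to change.** 1. **Before assignment (Sections 8.1 and 8.2).** Record each participant's decision as continuing or not continuing, for both named drugs and not only Thiola. Use this classification in every analysis, whatever happens to thiol use later, so that comparisons within it remain randomised.
2. **Section 15.2 and the synopsis.** Replace the plain t-test with a linear model for the same outcome, containing arm and the thiol indicator as a pre-specified covariate.
3. **Section 7.1 and the synopsis.** Replace the optional wording with a pre-specified sensitivity estimate in participants not on thiols and a descriptive treatment-by-thiol contrast, both reported whatever they show. Bring Section 4.1 into line.
4. **Timing.** Fix all of this before the interim look.

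Stratifying the computer sequence by this factor, with blocks within stratum, is a reasonable optional addition. It addresses imbalance but does nothing about dilution; the non-user estimate is what addresses that.

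The cost is one recorded item, one model term and some SAP wording, with no more patients. The downside is that with few continuing users, the estimate in that group and the interaction contrast will be imprecise, so a null contrast must not be read as evidence of no interference. The clinical rule on who stops or continues thiols is left as it is.
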